7.4 Evaluation of Safety

Analyses will be performed for all patients having received at least one dose of study drug. The study will use the CTCAE v4.0 for reporting of non-hematologic adverse events and modified criteria for hematologic adverse events. Safety assessments will consist of monitoring and reporting adverse events (AEs) and serious adverse events (SAEs) that are considered related to vismodegib, all events of death, and any study specific issue of concern.

The Principal Investigator at the UCSF Coordinating Center will hold the role of Study Chair. The Study Chair is responsible for the overall conduct of the study and for monitoring its safety and progress at all participating sites. The Study Chair is responsible for ensuring that all AEs and SAEs that are observed or reported during the study, are collected and reported to the FDA, appropriate IRB(s), and Genentech, Inc. in accordance with CFR 312.32 (IND Safety Reports).

The study period during which all AEs and SAEs must be reported begins after informed consent is obtained and initiation of study treatment and ends 1 year following the last administration of study treatment or study discontinuation/termination, whichever is earlier. After this period, investigators should only report SAEs that are attributed to prior study treatment.

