7.6 Recording of an Adverse Event

All grade 3 and above adverse events will be entered into OnCore[®], whether or not the event is believed to be associated with use of the study drug. Data about these events and their severity will be recorded using the NCI CTCAE v4.0.

The Investigator will assign attribution of the possible association of the event with use of the investigational drug, and this information will be entered into OnCore[®] using the classification system listed below:

Relationship	Attribution	Description
Unrelated to investigational drug/intervention	Unrelated	The AE is clearly NOT related to the intervention
	Unlikely	The AE is doubtfully related to the intervention
Related to investigational drug/intervention	Possible	The AE may be related to the intervention
	Probable	The AE is likely related to the intervention
	Definite	The AE is clearly related to the intervention

Signs or symptoms reported as adverse events will be graded and recorded by the Investigator according to the CTCAE v 4.0. When specific adverse events are not listed in the CTCAE v 4.0 they will be graded by the Investigator as *none, mild, moderate* or *severe* according to the following grades and definitions:

- Grade 0 No AE (or within normal limits)
- Grade 1 Mild; asymptomatic or mild symptoms; clinical or diagnostic observations only; intervention not indicated
- Grade 2 Moderate; minimal, local, or noninvasive intervention (e.g., packing, cautery) indicated; limiting age-appropriate instrumental activities of daily living (ADL)
- Grade 3: Severe or medically significant but not immediately life-threatening; hospitalization or prolongation of hospitalization indicated; disabling; limiting self-care ADL
- Grade 4: Life-threatening consequences; urgent intervention indicated
- Grade 5: Death related to AE

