7.8 Adverse Events Monitoring

All adverse events, whether or not unexpected, and whether or not considered to be associated with the use of the study drug, will be entered into OnCore[®], as noted above.

The Investigator will assess all adverse events and determine reportability requirements to the UCSF Data and Safety Monitoring Committee (DSMC) and UCSF's Institutional Review Board (IRB); and, when the study is conducted under an Investigational New Drug Application (IND), to the Food and Drug Administration (FDA) if it meets the FDA reporting criteria..

All adverse events entered into OnCore[®] will be reviewed by the Helen Diller Family Comprehensive Cancer Center Site Committee on a weekly basis. The Site Committee will review and discuss at each weekly meeting the selected toxicity, the toxicity grade, and the attribution of relationship of the adverse event to the administration of the study drug(s).

In addition, all adverse events and suspected adverse reactions considered “serious,” entered into OnCore® will be reviewed and monitored by the Data and Safety Monitoring Committee on an ongoing basis and discussed at DSMC meetings which take place every six (6) weeks. For a detailed description of the Data and Safety Monitoring Plan for a Multicenter Study refer to Appendix 9.

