8.2 Study Endpoints

Primary Endpoint:

- The proportion of patients with local-regional control at 12 months from protocol therapy completion, defined as complete or partial response, with absence of PD (see section 7.2) within the irradiated PTV.

Secondary Endpoints:

- Estimate of the probability of PFS and OS 12 months after protocol therapy completion. PFS is measured until disease recurrence or death due to any cause, whichever occurs first.
- Number and attribution of all adverse events (including vital signs, physical findings, and clinical laboratory results, CTCAE, v 4.0) in patients who receive any amount of study drug and radiation therapy.
- For each toxicity, the maximum occurring grade will be tabulated for each patient. The results will be summarized by toxicities observed during vismodegib treatment alone, during concurrent vismodegib with radiation therapy, for 3 months immediately following the completion of protocol therapy and for up to 12 months after completion of protocol therapy. The focus will be on the proportion of patients experiencing \geq grade 3 toxicity during each of these intervals.
- Proportion of patients experiencing Grade 4-5 adverse events assessed to be definitely, probably, or possibly related to the induction or concurrent treatment components of the protocol regimen (that is not definitely related to disease progression).
- Proportion of patients discontinuing treatment due to toxicity during the concurrent administration of vismodegib and radiation therapy. For this endpoint, discontinuation is defined as $<$ 75% of planned radiation therapy delivered.
- Response rate per RECIST criteria in patients who complete initial combined therapy of the primary site and regionally involved areas in subjects with measurable disease prior to initiation of therapy at 3 months after completion of protocol therapy.
- Proportion of patients with a decrease of BCC within the irradiated PTV after completing all protocol therapy to estimate clinical response to vismodegib and radiation therapy.

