Adverse events reporting to the DSMC will include reports from both the UCSF Coordinating Center, as well as the participating sites. The DSMC will be responsible for monitoring all data entered in OnCore® at the UCSF Coordinating Center and the participating sites. The data (i.e. copies of source documents) from the participating sites will be sent electronically or faxed over to the UCSF Coordinating Center prior to the monitoring visits in order for the DSMC to monitor the participating site’s compliance with the protocol, patient safety, and to verify data entry.

Adverse Event Review and Monitoring

Adverse Event Monitoring

All Grade 3-5 Adverse Events, whether or not unexpected, and whether or not considered to be associated with the use of study drug, will be entered into OnCore[®], UCSF's Clinical Trial Management System.

All Grade 3-5 adverse events entered into OnCore[®] will be reviewed on a monthly basis at the UCSF Site Committee meetings. All clinically significant adverse events must be reported to the UCSF Coordinating Center by the participating sites within 10 business days of becoming aware of the event or during the next scheduled quarterly conference call, whichever is sooner. The UCSF Site Committee will review and discuss the selected toxicity, the toxicity grade, and the attribution of relationship of the adverse event to the administration of the study drug(s) from the UCSF Coordinating Center and the participating sites.

In addition, all suspected adverse reactions considered "serious" must be entered in OnCore[®] and reported to the UCSF Coordinating Center within 1 business day. The suspected adverse reactions considered "serious" will be reviewed and monitored by the Data and Safety Monitoring Committee on an ongoing basis and discussed at the DSMC meeting, which take place every six (6) weeks.

If a death occurs during the treatment phase of the study or within 30 days after the last administration of the study drug(s) and is determined to be related either to the investigational drug or any research related procedure, the Study Chair at the UCSF Coordinating Center or the assigned designee must be notified within 1 business day from the participating site(s) and the Study Chair must then notify the DSMC Chair or qualified alternate within 1 business day of this notification. The contact may be by phone or e-mail.

Increase in Adverse Event Rates

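### Adverse events are attributed once, to the investigational drug, but the grade 4-5 endpoint and the grade 3+ related-event summary need attribution to the whole drug-plus-radiation regimen

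*Combined protocol and SAP*

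**What the plan says.** **What is recorded.** Section 7.6: "The Investigator will assign attribution of the possible association of the event with use of the investigational drug". One five-level scale follows, from Unrelated to Definite. The label over its upper three levels is "Related to investigational drug/intervention", and the level descriptions refer to the intervention, a term that is not defined. Section 4.1, on investigational drugs, describes only vismodegib.

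**What is reviewed.** Under 7.8 the Site Committee discusses relationship to the study drug. Appendix 9 likewise has it discuss "the attribution of relationship of the adverse event to the administration of the study drug(s) from the UCSF Coordinating Center" and the participating sites. Section 7.4 and the abstract describe safety assessment in terms of "adverse events (AEs) and serious adverse events (SAEs) that are considered related to vismodegib", together with deaths and study-specific issues of concern.

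**What the endpoints need.** The grade 4-5 endpoint in 8.2 (also in 2.2 and 2.3.2) counts patients with events "assessed to be definitely, probably, or possibly related to the induction or concurrent treatment components of the protocol regimen". Section 8.5 uses the proportion of patients with grade 3 or higher events related to the treatment components. The any-grade related-event endpoint (2.2, 2.3.2) is narrower: it names vismodegib or its combination with radiation, not radiation alone.

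**What does not use attribution.** Section 7.6 enters every grade 3 or higher event regardless of cause. Section 8.2 tabulates maximum grade per toxicity per patient by treatment interval. Section 8.4 limits grade 4-5 toxicity to 20% of patients and names no cause.

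**The concern.** The variable collected is not the one that two safety summaries are defined on. The concurrent component is vismodegib plus radiation, so an event caused by radiation alone meets the grade 4-5 definition in 8.2. If the investigator follows the sentence in 7.6 and judges that vismodegib clearly played no part, the same event is coded Unrelated and is not counted.

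Two consequences follow. The error runs one way, since the drug-only reading removes qualifying events and adds none. And because the scale label can be read more widely than the sentence above it, two sites can code the same event in opposite ways, so the pooled proportion has no fixed meaning.

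A single attribution also cannot show whether an event came from the drug, the radiation or their interaction. Section 4.2 expects radiation effects on wound healing might be intensified by vismodegib and undertakes to track them carefully.

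**Working it through.** The plan gives no figure for attribution or for the rate of regimen-related severe events, so there is none to reproduce. Its sample-size figure concerns efficacy and is unaffected: with 24 patients, 60% versus 80%, and success at 18 or more, the exact binomial test has one-sided type I error 0.096 and power 0.811, matching the stated 81% in 8.3.1.

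**Step 1: code three grade 4 events during concurrent treatment under each reading of 7.6.**

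| Event as judged by the investigator | Drug-only reading (sentence in 7.6) | Wider reading (scale label) | Meets grade 4-5 endpoint (8.2)? | Meets any-grade endpoint (2.3.2)? |
|---|---|---|---|---|
| Possibly due to vismodegib | Possible: counted | Possible: counted | Yes | Yes |
| Due to radiation, possibly intensified by vismodegib | Possible: counted | Possible or higher: counted | Yes | Yes |
| Due to radiation, clearly not vismodegib | Unrelated: not counted | Probable or Definite: counted | Yes | No, radiation alone is not named |

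The third row is the problem. Under the drug-only reading it is lost from the grade 4-5 endpoint and from the 8.5 summary. Under the wider reading it is kept there, but the same code would bring it into the any-grade endpoint, whose wording does not include it. No single field serves both definitions. The first two rows can also receive identical codes, so drug effect and interaction cannot be separated.

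**Step 2: size, as an illustration only.** Let p be the true proportion of patients with a regimen-related grade 4-5 event. Let f be the share of those patients whose only such events are due to radiation and are coded unrelated. Then

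recorded proportion = p × (1 − f).

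Both p and f are assumptions; the documents give neither.

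| p | f = 25% | f = 50% | f = 75% |
|---|---|---|---|
| 10% | 7.5% | 5.0% | 2.5% |
| 20% | 15.0% | 10.0% | 5.0% |
| 30% | 22.5% | 15.0% | 7.5% |

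For example, 0.20 × (1 − 0.75) = 0.05. If only some sites use the drug-only reading, the recorded value lies between p × (1 − f) and p. Proportions are used because safety is analysed in everyone given study drug (3.2, 8.6), not in the 24 evaluable patients.

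**Step 3: check the outputs that do not use attribution.** The 7.6 database entry, the 8.2 maximum-grade tabulation and the 8.4 rule all include the third-row event, however it is coded.

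**The case against.** The strongest reply is that little is lost. All grade 3 and higher events are entered, and 8.2 puts its focus on grade 3 or higher toxicity by interval with no attribution filter. Section 7.4 also requires all adverse events to be reported, and 7.9 requires sites to report all serious ones. The scale descriptions speak of the intervention, and radiation is described in the chapter headed Study Drugs, so a site could include it. Even on the drug-only reading, Possible is enough to count, and many skin events during daily concurrent dosing might be coded so. The case report form is not in the documents, so a single field is inferred from 7.6.

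Most of this stands, and it confines the point to the attribution-based summaries. It does not remove the point. The wider reading conflicts with the sentence introducing the scale, and having both readings available is what allows sites to differ.

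A reader might go further and infer three things that the documents do not support:

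- **The interim safety rule would miss radiation toxicity.** Section 8.4 names no attribution, so as written it counts these events.
- **Safety monitoring is confined to vismodegib-related events.** Section 7.4 also covers deaths and study-specific issues and requires reporting of all adverse events.
- **Severe radiation injury is the main severe toxicity expected.** Section 4.2 lists serious radiation damage as less likely.

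**Conclusion.** The mismatch is real and should be corrected. As written, the attribution in 7.6 cannot reliably deliver the grade 4-5 endpoint or the 8.5 grade 3+ related-event summary, and where the drug-only reading is followed both are biased toward apparent safety. The any-grade endpoint differs: leaving out events due to radiation alone agrees with its wording.

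The size is unknown. Over the assumed range (true rate 10-30%, 25-75% of affected patients lost), the recorded rate is between three quarters and one quarter of the true one. This rests on two assumptions: that the form follows 7.6 with one attribution per event, and that some severe events will be judged due to radiation and clearly not to vismodegib.

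The primary endpoint, the sample size, the maximum-grade tabulation and the interim rule are unaffected.

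**What to change.** 1. In 7.6 and on the adverse event form, record three attributions per event on the existing five-level scale: to vismodegib, to radiation, and to the combination. Replace or define the term intervention.
2. State the counting rules. Possible or higher on any of the three counts for the grade 4-5 endpoint (2.2, 2.3.2, 8.2) and the 8.5 grade 3+ summary. Possible or higher on vismodegib or the combination counts for the any-grade endpoint in 2.2 and 2.3.2.
3. Align 7.4, the abstract, 7.8 and Appendix 9, so that relatedness refers to protocol therapy and the Site Committee reviews all three attributions.
4. Keep the vismodegib attribution for reporting to the manufacturer, where 7.9 sets different timelines for related and unrelated serious events.

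Section 8.4 needs no change on this account.

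The cost is two extra form fields and wording edits. Telling radiation from combination will often be uncertain for a single event, but the any-of-three rule means that the grade 4-5 endpoint does not depend on that distinction. The fields should be in place before data collection, because attribution is hard to reconstruct afterwards.

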7.7 Follow-up of Adverse Events

All adverse events will be followed with appropriate medical management until resolved. Patients removed from study for unacceptable adverse events will be followed until resolution or stabilization of the adverse event. For selected adverse events for which administration of the investigational drug was stopped, a re-challenge of the subject with the investigational drug may be conducted if considered both safe and ethical by the Investigator.

7.8 Adverse Events Monitoring

All adverse events, whether or not unexpected, and whether or not considered to be associated with the use of the study drug, will be entered into OnCore[®], as noted above.

The Investigator will assess all adverse events and determine reportability requirements to the UCSF Data and Safety Monitoring Committee (DSMC) and UCSF's Institutional Review Board (IRB); and, when the study is conducted under an Investigational New Drug Application (IND), to the Food and Drug Administration (FDA) if it meets the FDA reporting criteria..

All adverse events entered into OnCore[®] will be reviewed by the Helen Diller Family Comprehensive Cancer Center Site Committee on a weekly basis. The Site Committee will review and discuss at each weekly meeting the selected toxicity, the toxicity grade, and the attribution of relationship of the adverse event to the administration of the study drug(s).

In addition, all adverse events and suspected adverse reactions considered “serious,” entered into OnCore® will be reviewed and monitored by the Data and Safety Monitoring Committee on an ongoing basis and discussed at DSMC meetings which take place every six (6) weeks. For a detailed description of the Data and Safety Monitoring Plan for a Multicenter Study refer to Appendix 9.

7.9 Expedited Reporting

Participating sites reporting to Study Chair

In addition to complying with all applicable regulatory reporting laws and regulations, each site will report the following information in writing to the Sponsor-Investigator within one business day of the Investigator’s awareness of occurrence:

- All SAEs
- Reports of pregnancy exposure (pregnancy encompasses the entire course of pregnancy and delivery, perinatal and neonatal outcomes, even if there were no abnormal findings; both maternal and paternal exposure is collected);
- Reports of lactation exposure;
- Overdose (with or without an SAE);
- Abuse (use for non-clinical reasons with or without an SAE);
- Inadvertent or accidental exposure; and
- Follow-up information regarding any of the above.
- The participating investigator should include his or her assessment of the causal relationship between each SAE and the study treatment.

Death from any cause while a patient is receiving protocol treatment and up to 30 days after the end of protocol must be telephoned and reported within ten days of discovery. Death related to surgery, regardless of the interval from surgery, must be reported by telephone within 10 days of discovery.

Reports will include the cover page provided, and reference the Protocol Number.

A copy of the report should be sent to the coordinating center CRC at UCSF. Information will be provided.

Reporting to the Data and Safety Monitoring Committee

If a death occurs during the treatment phase of the study or within 30 days after the last administration of the study drug(s) and it is determined to be related either to the study drug(s) or to a study procedure, the Investigator or his/her designee must notify the DSMC Chair (or qualified alternate) within 1 business day of knowledge of the event. The contact may be by phone or e-mail.

Reporting to UCSF Committee on Human Research (Institutional Review Board)

The Principal Investigator must report events meeting the UCSF IRB definition of “Unanticipated Problem” (UP) within 10 business days of his/her awareness of the event.

Reporting to Genentech or Roche

Study investigators must report all SAEs to Genentech or Roche within the timelines described below. The completed IND Safety Reports submitted to the FDA/Medwatch/case report should

be faxed immediately upon completion to Genentech Drug Safety at:

- Relevant follow-up information should be submitted to Genentech Drug Safety as soon as it becomes available.
- If a female subject becomes pregnant while receiving the study drug or within 24 months after the last dose of study drug, a report should be completed and expeditiously submitted to the Genentech. If a male subject receiving study drug (or within 3 months after the last dose of study drug) impregnates a female partner, then the female partner will be requested to provide informed consent to permit a report of the pregnancy to be completed and expeditiously submitted to Genentech.

Follow-up to obtain the outcome of the pregnancy should also occur. Abortion, whether accidental, therapeutic, or spontaneous, should always be classified as serious, and expeditiously reported as an SAE. Similarly, any congenital anomaly/birth defect in a child born to a female subject exposed to the vismodegib should be reported as an SAE.

Additional information on any vismodegib-exposed pregnancy and infant will be requested by Roche Drug Safety at specific timepoints (i.e., after having received the initial report, at the end of the second trimester, 2 weeks after the expected date of delivery, and at 3, 6, and 12 months of the infant's life).

- Serious AE reports that are related to the vismodegib and AEs of Special Interest (AESI) (regardless of causality) will be transmitted to Genentech within fifteen (15) calendar days of the Awareness Date.
- Serious AE reports that are unrelated to the vismodegib will be transmitted to Genentech within thirty (30) calendar days of the Awareness Date.
- Additional Reporting Requirements to Genentech include the following:
 - Any reports of pregnancy following the start of administration with the vismodegib will be transmitted to Genentech within thirty (30) calendar days of the Awareness Date.
 - All Non-serious Adverse Events originating from the Study will be forwarded in a quarterly report Genentech.
 - All IND annual reports submitted to the FDA by the Sponsor-Investigator should be copied to Genentech.

Refer to Appendix 11 for Genentech safety reporting fax cover sheet.

Study Close-Out

Any study report submitted to the FDA by the Sponsor-Investigator should be copied to Genentech. This includes all IND annual reports and the Clinical Study Report (final study report). Additionally, any literature articles that are a result of the study should be sent to Genentech. Copies of such reports should be mailed to the assigned Clinical Operations contact for the study:

8 Statistical Considerations and Evaluation of Results

